### 6.2. Secondary endpoints

The secondary endpoints of this study are:

- 1) optimized MRDTI scan sequences for SVT;
- 2) the assessment of interobserver agreement between the reviewers.

## 7. Data analysis

### 7.1 Sample size calculation

A sample size of 35 patients in each of groups 1 and 2 was chosen because with this sample size and an expected sensitivity of greater than 90%, the 95% confidence intervals on the point estimates would have a bandwidth of approximately  $\pm 15\%$ , ensuring that the point estimate was sufficiently accurate to make decisions about the appropriateness and safety of a future management study. To optimize the MRDTI scan sequences before the start of including patients in group 1 and 2, 3-5 patients with confirmed SVT will be included. If a reproducible clearly positive DTI signal is achieved in all three patients, the study can proceed with the inclusion of cohort 1 and 2. The final sample size is thus 73-75 patients. It is predetermined that at least five patients of each group (PVT, SpVT and BCS) will be included.

We expect that the required sample size is met within a time frame of three years. This expectation is based on the actual number of cases of acute SVT being diagnosed in the two study sites and considering that the number of chronic SVT diagnosis exceeds that of acute SVT. The Varese University Hospital is a tertiary referral center for SVT, and the LUMC is home to both a large oncology as well as organ transplantation departments where the diagnosis of SVT is made frequently.

## 7.2 Data analysis

### 7.2.1. Primary endpoint

A diagnosis (acute SVT, no signs of acute SVT, or non-diagnostic) for each arm of interest based on an aggregate reading of the MRDTI images will be made by two independent expert readers. A third reader will be involved to resolve any dispute. The sensitivity of MRDTI is determined by calculating the proportion of scans that are read as "positive for acute SVT" in patients with a confirmed acute SVT and the specificity is determined by calculating the proportion of scans that are read as "no signs of acute SVT" in patients with chronic SVT. The corresponding exact 95% confidence interval for each of the point estimates will be calculated. In addition to these estimates, sensitivity and specificity estimates with corresponding 95% confidence intervals will be calculated for the initial independent assessment of each of the two readers participating. A point estimate of the sensitivity of >90% will be acceptable for initiating a future management study.

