Sample size consideration	A sample size of 35 patients in each of groups 1 and 2 was chosen because with this sample size and an expected sensitivity of greater than 90%, the 95% confidence intervals on the point estimates would have a bandwidth of approximately $\pm 15\%$ , ensuring that the point estimate was sufficiently accurate to make decisions about the appropriateness and safety of a future management study. To optimize the MRDTI scan sequences before the start of including patients in group 1 and 2, 3 patients with confirmed SVT will be included. If a reproducible clearly positive DTI signal is achieved in all three to five patients, the study can proceed with the inclusion of cohort 1 and 2. The final sample size is thus 73-75 patients.
Statistical analysis	Primary analysis A diagnosis (acute SVT, no signs of acute SVT, or non-diagnostic) for each arm of interest based on an aggregate reading of the MRDTI images will be made by two independent expert readers. A third reader will be involved to resolve any dispute. The sensitivity of MRDTI is determined by calculating the proportion of

	
scans that are read as "positive for acute SVT" in patients with a confirmed acute SVT and the specificity is determined by calculating the proportion of scans that are read as "no signs of acute SVT" in patients with chronic SVT. The corresponding exact 95% confidence interval for each of the point estimates will be calculated. In addition to these estimates, sensitivity and specificity estimates with corresponding 95% confidence intervals will be calculated for the initial independent assessment of each of the two readers participating. A point estimate of the sensitivity of >90% will be acceptable for initiating a future management study.
 
Secondary analyses
 
For the optimization of the MRDTI scan sequences 3-5 pilot patients will be tested. The final sequences will be used in the 2 study groups when the study PI's all agree that the accuracy and quality of the sequences is adequate
 
For the interobserver agreement between the two reviewers a kappa statistic will be assessed. According to established criteria, a kappa score above 0.8 is considered excellent reliability, a score between 0.6 and 0.8 is considered good reliability, a score between 0.4 and 0.6 is considered moderate reliability and a score below 0.4 is considered poor reliability.

--	---

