## 4.2 Definition of SVT

### 4.2.1. *Acute Splanchnic vein thrombosis*

Acute splanchnic vein thrombosis is defined as acute symptomatic or acute incidental asymptomatic thrombosis in the mesenteric, splenic, portal or hepatic veins.

Acute symptomatic thrombosis refers to acute onset (< 2 week existent) of symptoms characteristic for SVT thrombosis (including but not limited to abdominal pain) with SVT confirmed with DUS, CTA or MRA, dependent on the anatomical location. Acute incidental asymptomatic thrombosis refers to an incidentally detected SVT with DUS, CTA or MRA, absent on previous diagnostic tests performed in the last 2 weeks before the new incidental finding, in patients without symptoms characteristic of SVT.

The diagnosis of SVT can be made with DUS, CTA and MRA. The diagnosis SVT is defined as the absence of flow in the involved vein (mesenteric, splenic, portal or hepatic vein) as well as the hyperechogenic thrombus inside the lumen seen on DUS. Acute SVT on CTA is defined as a non-enhancing filling defect in the lumen of the involved vein and possibly increased enhancement of hepatic ischemic areas during the arterial phase and decreased enhancement in portal phase. At MR imaging, acute SVT is isointense on T1-weighted images and hyperintense on T2-weighted images.[1]

DUS is the current first line imaging test of choice for the diagnosis of PVT and BCS. However, when DUS is inconclusive MRA/MRP or CTA serves as reference test for the diagnosis of both PVT and BCS. For the diagnosis of SpVT, DUS is the first choice imaging test, however in a non-diagnostic test result, contrast enhanced CT will serve as the reference test.

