### **4.3. MRDTI**

MRDTI will be performed as described before with a 1.5 or 3.0 Tesla unit using a T1-weighted magnetisation prepared three-dimensional gradient-echo sequence. The sequence includes a water-only excitation radiofrequency pulse to abolish the fat signal, and the effective inversion time is chosen to nullify the blood signal. Imaging will be performed of the affected veins in two imaging blocks with a total acquisition time of 8-12 minutes by using a 55-cm body coil.

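### The primary reading is defined for an undefined 'arm of interest', and a true positive need not lie in the thrombosed vein, so sensitivity could be slightly inflated

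*Combined protocol and SAP*

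**What the plan says.** Section 7.2.1 (Primary endpoint) says that two independent readers will make a diagnosis "for each arm of interest based on an aggregate reading of the MRDTI images", with a third reader for disputes. The synopsis has the same phrase: "A diagnosis (acute SVT, no signs of acute SVT, or non-diagnostic) for each arm of interest". Neither place says what an arm is.

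Sensitivity is then the "proportion of scans that are read as 'positive for acute SVT' in patients with a confirmed acute SVT", and specificity is the "proportion of scans that are read as 'no signs of acute SVT' in patients with chronic SVT". Each gets an exact 95% interval. A sensitivity point estimate above 90% is acceptable for starting a management study.

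The disease is defined by named veins. Section 4.2.1 describes acute SVT as "acute symptomatic or acute incidental asymptomatic thrombosis in the mesenteric, splenic, portal or hepatic veins", and the ultrasound and CT criteria in that section refer to the particular vein involved. Section 4.3 says: "Imaging will be performed of the affected veins in two imaging blocks". No section asks the readers to record which vein they called acute, and none compares that vein with the one on the reference test.

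**The concern.** Two things in the definition of the primary endpoint look wrong.

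- **The reading unit has no meaning here.** The target veins are portal, mesenteric, splenic and hepatic. The only other anatomical use of the word arm in the body text is in section 2.4.2, about arm vein thrombosis, a different disease. Reading it as study arm does not help: the protocol calls its patient sets groups or cohorts, and the readers are blinded to the diagnosis that defines them.
- **The true-positive rule ignores location.** Suppose the reference test shows a portal vein thrombus, and the readers miss it but call an acute thrombus in the splenic vein. The scan is labelled positive in a confirmed case and counts towards sensitivity, although the test failed to detect the thrombus in question.

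Such an error can only raise sensitivity. In a control, an acute call in any vein already counts against specificity. Sensitivity is also the sole number in the go rule, and with 35 cases that rule can turn on one patient.

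**Working it through.** **Inputs.** 35 cases and 35 controls (section 7.1); exact 95% interval and go rule above 90% (section 7.2.1); MRDTI specificity in leg DVT of 91% to 100% (section 2.4.1). The documents give no frequency of calls in the wrong vein, so that is an assumption below.

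**Plan's own figure.** Section 7.1 expects intervals of about ±15% with 35 patients and sensitivity above 90%. The smallest count above 90% is 32/35 = 91.4%, because 31/35 = 88.6%. The Clopper-Pearson interval for 32/35 is 76.9% to 98.2%, so the lower limit lies 14.5 points below the estimate. The figure is reproduced as the distance to the lower limit. The present point does not depend on it.

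**Effect of one wrong-vein call.** Each adds 1/35 = 2.9 points under the written rule. With matching required:

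| Scans read positive | Written rule | One wrong-vein call removed | Two removed |
|---|---|---|---|
| 32 | 91.4%, go | 31/35 = 88.6% (73.3 to 96.8), no go | 30/35 = 85.7% (69.7 to 95.2), no go |
| 33 | 94.3%, go | 32/35 = 91.4%, go | 31/35 = 88.6%, no go |
| 34 | 97.1%, go | 33/35 = 94.3%, go | 32/35 = 91.4%, go |

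**How often this might happen.** Let s be the true sensitivity with matching, and f the share of scans missing the true vein that are called acute in another vein. The expected number of wrong-vein positives is 35 × (1 − s) × f. As an assumption, let the two errors be independent and let f equal one minus the leg-DVT specificity, i.e. 0 to 0.09:

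- s = 0.90: 35 × 0.10 × 0.09 = 0.3 at most
- s = 0.85: 35 × 0.15 × 0.09 = 0.5 at most
- s = 0.80: 35 × 0.20 × 0.09 = 0.6 at most

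In each case this is less than one patient.

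**Effect on the go decision.** Under the written rule the probability that a case is scored positive is s + (1 − s)f. The probability of at least 32 of 35 is:

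| s | f = 0 (matching) | f = 5% | f = 10% | f = 20% |
|---|---|---|---|---|
| 0.85 | 20.9% | 24.5% | 28.6% | 38.1% |
| 0.80 | 6.1% | 7.9% | 10.3% | 16.7% |

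The columns at 10% and 20% lie above the range implied by the leg-DVT figures and only show how the effect grows.

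**The case against.** The strongest reply is that the odd phrase is stray wording and the unit is in fact fixed. The sensitivity and specificity sentences count scans in patients, section 7.1 sizes the groups in patients, and the study schedule has one MRDTI visit per patient. This stands. A reader might infer that arm means vein, so that several correlated veins from one patient enter an exact binomial interval that assumes independence. The documents do not support that: the denominators are one scan per patient.

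A reader might also infer that specificity needs its own vein rule. It does not. A control scan read as showing no signs of acute SVT already implies that no vein was called acute.

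The next reply is that section 4.3 directs imaging at the affected veins and that the bias needs a miss and a false call in the same patient. This stands as a limit on frequency. It does not close the gap: section 4.3 describes acquisition, neighbouring veins may lie within the imaging blocks, and no reading rule confines the call to the reference vein. Equally, neither the plural 'veins' nor the coil size shows that unaffected veins will be read in every patient.

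A third reply is that any single reclassified patient flips 31/35 to 32/35. That is true, so the flip shows how fragile the rule is at the margin, not how large this bias is.

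Finally, matching has its own cost. The protocol reports imperfect reference tests: ultrasound sensitivity of 79-90% for mesenteric thrombosis (section 2.2.2) and CT sensitivity of 71% for splenic thrombosis (section 2.2.3). MRDTI could be right in a vein that the reference missed. This is a good reason to report both estimates.

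**Conclusion.** The point holds as a modest, cheaply corrected weakness in the primary endpoint definition. The reading unit is misnamed in both places where it appears, and the written rule allows an acute call in the wrong vein to count as a true positive. Sensitivity could therefore be inflated, by 2.9 points per affected patient, and one such patient decides the go rule when the matched count is 31.

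It would go too far to say that sensitivity is materially biased upward. The frequency is not in the documents. With leg-DVT specificity carried over, independent errors and a true sensitivity of 80% to 90%, fewer than one such patient is expected among 35. The direction of the error is certain; its size rests on those assumptions.

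**What to change.** 1. In section 7.2.1 and the synopsis, replace 'for each arm of interest' with 'for each patient'.
2. Have the readers, still blinded to the final diagnosis, record the vein or veins they call acute. Send two acute calls that share no vein to the third reader as a dispute.
3. For the go rule, count a group 1 patient as a true positive only if at least one vein with thrombus on the reference test is called acute.
4. Report the any-vein sensitivity beside it with its exact interval, and list each discordant patient with the reference vein and the called vein.

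The specificity rule and the denominators can stay as written.

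The cost is a few sentences and one field on a reading form. Reading is post hoc, so no extra scans or patients are needed. Sensitivity may come out slightly lower, and a patient in whom MRDTI correctly finds a thrombus that the reference test missed could be scored as a false negative. The any-vein estimate and the list of discordant cases make that visible.

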### 7.2.2. Secondary analyses

For the optimization of the MRDTI scan sequences 3 pilot patients will be tested. The final sequences will be used in the 2 study groups when the study PI's all agree that the accuracy and quality of the sequences is adequate.

For the interobserver agreement between the reviewers a kappa statistic will be assessed. According to established criteria, a kappa score above 0.8 is considered excellent reliability, a score between 0.6 and 0.8 is considered good reliability, a score between 0.4 and 0.6 is considered moderate reliability and a score below 0.4 is considered poor reliability.

## **7.3 Data management**

### *7.3.1. Data collection*

Data will be collected, used and stored, which concerns data such as name, address, date of birth and medical information. Diligent efforts will be made to ensure the study data are stored securely and confidential information is protected. The handling of personal data will comply with the General Data Protection Regulation (GDPR).

All study participants will receive a study number which is a unique identifier (not based on patient initials and birth date). The key to the code will be safely stored in the local research institute and safeguarded by the principal investigator. The unique study number will be used on the CRF and with the MR images stored in the radiology database. The data that will be sent to the sponsor will only contain the code and not names or other data that can identify study participants. All electronic data and records will be saved under their unique study number and stored in a secured file on the computer. Access to study files and electronic records will be restricted to authorized study personnel. The local investigators are responsible for ensuring that all sections of the eCRF are completed correctly, and that entries can be verified against source data.

### *7.3.2. Data handling*

The electronic data entry system allows the principle investigators to control the entry process with the help of the built-in review functions. Any missing data or inconsistencies will be reported back to

the respective site and clarified by the responsible investigator. The principle investigators are authorized, in the case of discrepancies or correction of data errors, to directly contact the responsible person at the study site. After completion of data entry and if no further corrections are to be made in the database, the access rights will be withdrawn, and the database will be declared closed and used for statistical analyses.

#### *7.3.3. Storage and Archiving of Data*

The principle investigators will archive all study data (subject identification code list, source data, and investigator's files) and relevant correspondence in the Investigator Site File and this is archived in a closed storage cabinet. Only the principle investigator has access to the subject identification code list and source data. The monitor which has been hired by the sponsor of the study and the Healthcare and Youth Inspectorate also have access to the data in case of safety reviewing. The Investigator Site File, all source data, and other pertinent documents will be archived for 15 years at the research location.

#### *7.3.4. Withdrawing consent*

Study participants can withdraw their consent to the use of the personal data at any time. The study data collected until the moment of the withdraw can be used in the study.

#### *7.3.5. Processing data*

The principle investigator and coordinating investigator of the study in the LUMC are responsible for the processing of personal data of the study participants. For questions about rights concerning processing data study participants can contact the principal and coordinating investigators or Data Protection Officer of the LUMC or the Dutch Data Protection Authority.

## 8. Ethical considerations

### 8.1 Regulatory statement

The study protocol and consent forms will be submitted to the Research Ethics Committee. Patient recruitment will not commence before formal approval has been granted. The study will be conducted according to the principles of the "Declaration of Helsinki" (as amended in Tokyo, Venice and Hong Kong, Somerset West and Edinburgh) and in accordance with the Guidelines for Good Clinical Practice (CPMP/ICH/135/95 - 17th July 1996). The study will be carried out in keeping with local legal and regulatory requirements.

### 8.2 Inclusion and consent

Before being admitted to the study, the subject must consent to participate after being fully informed about the nature, scope, and possible consequences of participation. The consent documents must be in a language understandable to the subject and must specify who informed the subject. After reading the informed consent document, the subject must give consent in writing. The subject's consent must be confirmed by the personally dated signature of the subject and by the personally dated signature of the person conducting the informed consent discussions. A copy of the signed informed consent document must be given to the subject. The original signed consent document will be retained by the investigator.

The investigator will not undertake any measures specifically required only for the clinical study until valid consent has been obtained. All participants will be told that participation is voluntary and they are free to leave the study at any time. Because the timeframe for patient recruitment and imaging are critical to the success of the study, research personnel will maintain regular communication with staff in clinical areas where eligible patients are likely to be recruited. After they

have given written acknowledgement of informed consent to participate, a medical screening will take place. Through patient interview and review of medical records, it will be confirmed that they satisfy all inclusion criteria and do not meet any of the exclusion criteria.

### **8.3 Confidentiality**

The name of the subjects and other confidential information are subject to medical professional secrecy. For the primary and secondary analysis, only anonymized information that is included in the standardized paper CRF forms can be used. This information is depersonalized and stored under an individual identification code that is assigned to each patient at inclusion after signing informed consent. The study patients will declare in the written consent to release the investigator from the medical professional secrecy to allow identification of subject's name and/or inspection of original data for monitoring purposes by health authorities and authorized persons (monitors).

The investigator will maintain a personal subject identification list (subject numbers with the corresponding subject names) to enable records to be identified. Study findings stored on a computer will be kept safe in accordance with local data protection laws and will be handled in strictest confidence. For protection of these data, organizational procedures are implemented to prevent distribution of data to unauthorized persons. The appropriate regulations of data legislation will be fulfilled in its entirety.

### **8.4 Responsibilities of principal investigators**

The principal investigators will ensure that all persons assisting with the study are adequately informed about the protocol, any amendments to the protocol, and their study-related duties and functions. The principal investigators will maintain a list of sub-investigators and other appropriately qualified persons to whom they have delegated significant study-related duties.

## **8.5 Approval of Study Protocol**

Before the start of the study, the study protocol, informed consent document, and any other appropriate documents will be submitted to the independent ethics committee/institutional review board of the LUMC in Leiden. The document of final approval by the independent ethics committee should mention the title of the study, the study code, all study sites, the documents they reviewed, and the date of decision. Before the first subject is enrolled in the study, all ethical and legal requirements must be met. The investigator must keep a record of all communications with the independent ethics committee and the competent authorities.

## **8.6 Ongoing information for independent ethics committee**

### *8.6.1. Amendments*

The competent authorities including the independent ethics committee must be informed of all subsequent protocol amendments and administrative changes, in accordance with the respective local legal requirements. Amendments must be evaluated to determine whether formal approval should be sought and whether the informed consent document should also be revised. The independent ethics committee must be informed of all subsequent protocol amendments which require formal approval in accordance with the legal requirements.

